4.1.1 Missing Assessments and Not Evaluable Designation

When no imaging/measurement is done at all at a particular time point, the subject is **not evaluable (NE)** at that time point. If only a subset of lesion measurements is made at an assessment, the case is also considered NE at that time point, unless a convincing argument can be made that the contribution of the individual missing lesion(s) would not have changed the assigned time point response.

4.1.2 Confirmation Scans

Verification of Response: Confirmation of PR and CR is required at least 4 weeks later to ensure that the responses identified are not the result of measurement error.

4.2 Best Overall Response: All Time Points

The best overall response is determined once all the data for the subject are known. It is the best response recorded from the start of the study treatment until objectively documented progression per RECIST Criteria or subsequent cancer therapy, whichever happens first, taking into account any requirement for confirmation. The subject's best overall response assignment will depend on

the findings of both target and non-target disease and will also take into consideration the appearance of new lesions.

Best response is defined as the best response across all time points with subsequent confirmation. CR or PR may be claimed only if the criteria for each are met at a subsequent time point as specified in the protocol (generally 4 weeks later).

In this circumstance, the best overall response can be interpreted as specified in Table 4.2-1. When SD is believed to be the best response, it must meet the protocol-specified minimum time from baseline. Measurements must have met the SD criteria at least once after study entry at a minimum interval (in general, not less than 6 weeks).

Table 4.2-1: Best Overall Response When Confirmation of CR and PR Is Required

Overall Response		Best Overall Response
First Time Point	Subsequent Time Point	
CR	CR	CR
CR	PR	SD, PD, or PR ^a
CR	SD	SD provided minimum criteria for SD duration met, otherwise, PD
CR	PD	SD provided minimum criteria for SD duration met, otherwise, PD
CR	NE	SD provided minimum criteria for SD duration met, otherwise NE
PR	CR	PR
PR	PR	PR
PR	SD	SD
PR	PD	SD provided minimum criteria for SD duration met, otherwise, PD
PR	NE	SD provided minimum criteria for SD duration met, otherwise NE
NE	NE	NE

CR = complete response; NE = not evaluable; PD = progressive disease; PR = partial response; SD = stable disease.

^a If a CR is truly met at first time point, then any disease seen at a subsequent time point, even disease meeting PR criteria relative to baseline, makes the disease PD at that point (because disease must have reappeared after CR). Best response would depend on whether the minimum duration for SD was met. However, sometimes CR may be claimed when subsequent scans suggest that small lesions were likely still present and in fact the subject had PR, not CR, at the first time point. Under these circumstances, the original CR should be changed to PR, and the best response is PR.

4.3 Duration of Response

4.3.1 Duration of Overall Response

The duration of overall response is measured from the time measurement criteria are first met for CR/PR (whichever is first recorded) until the first date that recurrent disease or PD is objectively documented (taking as reference for PD the smallest measurements recorded on study).

The duration of overall CR is measured from the time measurement criteria are first met for CR until the first date that recurrent disease is objectively documented.

4.3.2 Duration of Stable Disease

SD is measured from the start of the treatment (in randomized trials, from date of randomization) until the criteria for progression are met, taking as reference the smallest sum on study (if the baseline sum is the smallest, this is the reference for calculation of PD).

APPENDIX 7 STATISTICAL METHODOLOGY

STATISTICAL DETAILS FOR BAYESIAN LOGISTIC REGRESSION METHOD (BLRM AND BLRM-COPULA) MODEL AND PRIORS FOR DOSE ESCALATION

1 MODEL SETUP FOR BMS-986242 MONOTHERAPY (LEAD IN)

1.1 Monotherapy Methodology Description

An adaptive 2-parameter Bayesian Logistic Regression Method (BLRM) model guided by the escalation with overdose control (EWOC) principle^{1,2,3} will be used to guide the dose escalation of BMS-986242 in the monotherapy lead-in phase and to provide dose recommendation during dose escalation.

The BLRM will be fitted on the dose-limiting toxicity (DLT) data during the first 2 weeks of treatment accumulated throughout the dose escalation to model the dose-toxicity relationship of BMS-986242 in the monotherapy lead-in phase.

The dose-toxicity relationship for BMS-986242 monotherapy is assumed to follow a logistic model:

$$\text{logit}(p_i) = \log(\alpha_1) + \beta_1 \log(d_{1i}/d_1^*),$$

where p_i is the probability of toxicity at dose level d_{1i} . Note that the α_1 and β_1 parameters are assumed positive and d_1^* is the reference dose for BMS-986242 (please refer to the meaning of α_1 and β_1 in Section 1.2.1 for detailed implementation).

1.2 Prior Specification for BMS-986242 Monotherapy

The Bayesian approach requires the specification of prior distributions for model parameters, which include parameters (α_1, β_1) for BMS-986242. The prior distributions for BMS-986242 single-agent activity were derived using a weakly informative prior, as well as discussion with the Bristol-Myers Squibb (BMS) clinical team.

Derivation of prior distribution of these parameters is provided in the following subsections.

1.2.1 Prior Derivation for BMS-986242 Parameters ($\log(\alpha_1)$, $\log(\beta_1)$)

A weakly informative prior will be used for parameters (α_1, β_1) for BMS-986242 to reflect the potential of the different toxicities of BMS-986242 and allow for considerable prior uncertainty.

Further details are provided below.

Weakly Informative Prior

- The median DLT rate at the reference dose (BMS-986242 at 600 mg QD) was assumed to be 30%, that is, mean($\log(\alpha_1)$) = $\text{logit}(0.3) = \log(0.3/(1-0.3)) = -0.847$.
- A doubling in dose was assumed to double the odds of DLT, that is, mean($\log(\beta_1)$) = 0.

The standard deviation of $\log(\alpha_1)$ was set to 1.53 using the following steps:

- If the toxicity probability range was set to be [1%, 99%], then the toxicity interval would be $\text{logit}(0.99) - \text{logit}(0.01) = 9.19$.

- To cover 99.7% of the variance, the toxicity interval will cover 6*standard deviation (SD) ($\log(\alpha_1)$), which gives us $SD(\log(\alpha_1)) = 9.19/6 = 1.53$.

Correspondingly, the standard deviation of $\log(\beta_1)$ was set to 1, which allows for considerably larger prior uncertainty for the dose toxicity.

- 1) The correlation between $\log(\alpha_1)$ and $\log(\beta_1)$ was set to 0.
- 2) $\log(\alpha_1)$ and $\log(\beta_1)$ follow a bivariate normal distribution.

Table 1: Prior Distribution for Model Parameters for BMS-986242

Parameter	Means	Standard Deviations	Correlation
$\log(\alpha_1), \log(\beta_1)$	(-0.847, 0)	(1.53, 1)	0

2 MODEL SETUP FOR BMS-986242 AND NIVOLUMAB COMBINATION

2.1 Methodology Description for Combination Therapy

Toxicity profiles of both BMS-986242 monotherapy and nivolumab monotherapy will be incorporated to develop the combination model framework. A copula-type model will be used to cover all general combination cases, including additive and synergistic effects. The combination of the 2 treatments will be explored using a Bayesian hierarchical model by utilizing the toxicity profiles of the single agents as prior marginal profiles for the combination. The following copula-type model⁴ will be used to describe the probability p_{ij} of toxicity when dose level i of agent A and dose level j of agent B are administered in combination:

$$p_{ij} = 1 - \exp\left(-\left[\{-\log(1 - p_i^m)\}^{1/\gamma_1} + \{-\log(1 - q_j^n)\}^{1/\gamma_1}\right]^{\gamma_1}\right),$$

where p_i is the prespecified best guess toxicity probability for agent A, q_j is the prespecified best guess toxicity probability for agent B, m and n characterize the individual drug effect, and γ_1 characterizes the drug-drug interactive effect.

The joint toxicity framework models the toxicity rates of both agents as well as their interaction effects in a 7-parameter hierarchical model, where each monotherapy dose-toxicity relationship will be characterized by a 2-parameter BLRM model (see [Section 1.1](#)). There are 3 additional parameters for the copula-type model, 1 for each agent (m and n) as well as 1 for the interaction term (γ_1). A dose-toxicity surface will be characterized for different dose combinations of these 2 agents.

As there are currently no historical data or prior knowledge to indicate how much information is to be borrowed for each of the single agents, parameters m and n are both set to be 1, meaning borrowing 100% of the information from the 2 agents. The above formula is then simplified into a 5-parameter model as follows:

$$p_{ij} = 1 - \exp\left(-\left[\{-\log(1 - p_i)\}^{1/\gamma_1} + \{-\log(1 - q_j)\}^{1/\gamma_1}\right]^{\gamma_1}\right).$$

Since only a fixed nivolumab dose (480 mg) will be used in the BMS-986242 and nivolumab combination, this surface will be simplified into a 2-dimensional dose-toxicity curve. Posteriors for the corresponding 5 parameters (2 logistic regression parameters $[\alpha_1, \beta_1]$ for BMS-986242 and 2 logistic regression parameters $[\alpha_2, \beta_2]$ for nivolumab, as well as 1 interaction parameter for the copula-type model $[\gamma_1]$, which will be discussed in detail in the following section) will be fitted into the in-house developed model. It implements the above-described theoretical setup.

2.2 Prior Specification for Combination Therapy

2.2.1 Marginal Prior for BMS-986242

Posterior information on $\log(\alpha_1)$ and $\log(\beta_1)$ from the monotherapy Lead in will be used as marginal BMS-986242 prior for combination with nivolumab. This prior information is not prespecified and will be continuously updated when additional DLT information from the monotherapy is available. In the simulation (see Section 3, the prior of BMS-986242 as described in Section 1.2.1 (Table 1) is used for illustration purposes because no real-time DLT data are available at this time.

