5.1.2.1 Part 1: Dose Escalation

Six disease-restricted populations will be included in the dose-escalation part. These are melanoma, NSCLC, SCCHN, RCC, BUC, and gastric cancer. The dose-escalation part of the study will evaluate doses of BMS-986242 in combination with nivolumab based on DLTs using a BLRM model (for BMS-986242 monotherapy lead-in) and BLRM-copula model (for BMS-986242 in combination with nivolumab). The Bayesian models will be used for recommendation of the next dose to be investigated. BLRM (combined with copula) framework with an escalation with overdose control principle will be employed to ensure that safety is not compromised during dose escalation.

The initial dose level of BMS-986242 will be 12.5 mg administered orally daily. After a 2-week period, once initial lead-in monotherapy (Cycle 0) is deemed tolerable, combination with 480 mg flat dose nivolumab (Cycle 1) will be initiated.

Dose levels to be considered for the next combination cohort (with monotherapy lead-in) will be based on recommended monotherapy dose from BLRM and recommended combination dose from BLRM-copula. The lower dose from these 2 recommendations will be considered. Potential dose levels for dose escalation are provided in [Table 5.1.2.1-1](#). The maximum allowable increase in dose will be 100%. Final dose selection for the next cohort/dose level will be made in conjunction with all data available from PK and pharmacodynamic assessments, and will be made after discussion and agreement between investigators and BMS Medical Monitor. Accordingly, intermediate or lower doses, or less frequent dosing of BMS-986242 may be tested if none of the planned doses/schedules are found to be tolerated as the lead-in phase or in combination with nivolumab.

Initially, approximately 4 participants will be treated at the starting dose level of BMS-986242. During the dose-escalation phase, once a dose level has been decided, a set of approximately 4 participants will be initially treated at that specified dose level. Increments of approximately 3 participants will be added to each dose level depending on model recommendation and clinical judgment. Due to the potential for early discontinuation, additional participant(s) may be enrolled to ensure at least 3 evaluable participants at each dose level.

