10 STATISTICAL CONSIDERATIONS

10.1 Sample Size Determination

10.1.1 Dose Escalation

During the dose-escalation trial, the sample size at each dose in these arms depends on observed toxicity and posterior inference.

Up to approximately 78 participants are planned to be enrolled for Part 1 (dose escalation) and clinical pharmacology substudy: approximately 30 participants for the dose-escalation phase, with up to 24 additional participants in Part 1 for additional characterization of the safety, PK, and pharmacodynamic profile of BMS-986242, and approximately 24 participants for the clinical pharmacology substudy (including food effect). [Appendix 7](#) provides additional details for the operating characteristics of the BLRM for monotherapy and BLRM-copula for combination therapy based on doses from 25 mg; an addition of 12.5 mg is expected to provide similar operating characteristics..

For the food effect assessment, the sample size is not based on statistical power for comparison but on consideration of the precision of the estimates of geometric means of C_{max} and AUC(0-T) of BMS-986242.

For a sample size of 6 participants, there is an 80% probability for the 90% confidence interval to be within 79.6% to 125.7% of the point estimate of the geometric mean for C_{max} and within 80.4% to 124.4% of the point estimate of the geometric mean for AUC(0-T). This calculation assumes that log(C_{max}) and log(AUC[0-T]) of BMS-986242 are normally distributed with a standard deviation (SD) of 0.23 and 0.22, respectively, as estimated from a study of a related compound.

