3.1 Simulation Parameters

One thousand trial simulations were used for each scenario. All simulations were run using EAST 6.3.1[®] software for BLRM model for BMS-986242 monotherapy and in-house developed code via R and Openbugs for BLRM-copula method for BMS-986242 in combination with nivolumab. The number of participants to be treated in each cohort in a specific dose level and the stopping rules used to declare MTD are defined as:

- Fixed cohort size: 3
- Probability of overdosing: < 25% for BLRM and 35% for BLRM-Copula
- Probability of achieving the target toxicity: > 50%
- Maximum number of participants treated: 30
- Minimum number of participants treated at a given dose level in order to declare MTD: 6
- Maximum number of participants at a dose: 12

The provisional dose levels for BMS-986242 monotherapy are 25 mg through 600 mg. For the combination therapy, nivolumab is fixed at 480 mg flat dose for Q4W.

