3.2.2 Operating Characteristics of BLRM-copula for Combination Therapy

Three hypothetical scenarios were investigated: (1) additive joint toxicity; (2) toxicity rates 25% higher than the additive scenario; (3) toxicity rates 50% higher than the additive scenario (Table 5).

Table 5: Simulation Results of BLRM-Copula for Combination

Scenario	BMS-986242 Dose	25	50	100	200	400	600	MTD not selected (%)	Fitted MTD	Toxicity Observed (%)	Avg # Pts
Additive	% DLT	12	14	17 ^a	23 ^a	32 ^a	40				
	% MTD	2.7	5.7	23.6	24.6	23.6	9.8	10	464.7	24.3	19.5
	# Pts	3.6	3.2	4.7	3.6	2.4	2.2				
	#DLT	0.5	0.4	0.7	0.8	0.7	0.9				
25% Higher	% DLT	15	18 ^a	21 ^a	29 ^a	40	50				
	% MTD	5.5	8.7	26.4	29.8	12.9	2.6	14.1	357.2	27.7	17.7
	# Pts	3.8	3.2	4.5	3.5	1.7	1.1				
	#DLT	0.6	0.6	0.9	0.9	0.7	0.6				
50% Higher	% DLT	18 ^a	21 ^a	26 ^a	34	48	60				
	% MTD	7.9	10.7	29.5	24.5	5.4	0.2	21.8	291.7	31.7	15.5
	# Pts	3.9	3.2	4.1	2.8	0.9	0.6				
	#DLT	0.7	0.7	1.0	0.9	0.5	0.3				

^a Doses with true target toxicity within the target toxicity interval [16%, 33%]

Note: % DLT = true DLT rate; % MTD = proportion of the dose selected as the MTD; #DLT = average number of DLTs; MTD not selected = dose was below lowest dose or above highest dose; Fitted MTD = fitted MTD at 33% as the target toxicity rate; Toxicity observed = Average proportion of DLTs out of all simulated trials; # Pts = average number of participants

The average sample size was around 20 participants. The results show how the EWOC principle limits the risk of exposing participants from unacceptable toxic dose levels. Overall, the scenarios illustrated above demonstrate that the model performs well by correctly identifying the MTD ranging from 49% to 72% in the hypothetical scenarios investigated while limiting participants from receiving unacceptable toxic dose levels.

[figure not shown]
4 INTERIM MONITORING CASE STUDY TO ILLUSTRATE PROVISION OF DOSE RECOMMENDATIONS DURING DOSE ESCALATION

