In order to provide a comprehensive view of the dynamics of the models, different hypothetical scenarios exploring different possibilities are examined. For the simplicity of illustration purposes, a static cohort size of 3 subjects is applied for dose level 25 mg. This cohort size could vary during the actual clinical trial, and the BLRM (-Copula) models are designed to fit various different cohort sizes, adaptively. In general, there are many possible scenarios for a specific dose level, especially with a monotherapy lead-in followed by combination treatment. For example, there could be 0, 1, 2, or 3 DLTs observed in the monotherapy lead-in period, and similarly 0, 1, 2, or 3 DLTs observed in the combination period.

During interim monitoring, posterior probabilities will be updated when there is new DLT information available. The following two visualization plots will be produced to reflect the real time dose-DLT relationship, to quantify benefit (in the form of target dosing) and risk (in the form of overdosing and underdosing) during the model’s recommendation process, and to facilitate clinical team’s interpretation of the model recommendations for the final decision making:

- Dose-DLT profile for the doses ranging between 0 mg and 600 mg (Figure 1).
- Stacking histograms displaying predictive probabilities on DLT rates classified into 3 different categories (Underdosing, Target Dosing and Overdosing) (Figure 2).

Figure 1: An Example of Updated Dose-DLT Profile After Incorporating Prior Information and DLT Information at 25 mg (0/3 DLTs in Monotherapy Lead-in and 0/3 DLTs in Combination at 25 mg for BMS-986242)

Interpretation and usage of Figure 1:

Figure 1 is a snapshot of an updated dose-DLT profile with DLT information available at dose level 25 mg after the combination period (assuming there was no DLT in either monotherapy lead-in or combination period). The dose-DLT profile is captured with a continuous dose spectrum ranging from 0 mg through 600 mg, which is a slice of the dose-DLT surface of the combination of two drugs with nivolumab fixed at 480 mg. For each dose within the range, there is a corresponding distribution of the predicted DLT rates calculated from the posterior samples of the

[figure not shown]
model parameters. This figure will be updated each time new DLT information becomes available from different dose levels.

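### Appendix 7 gives the interaction parameter a prior that no gamma distribution satisfies, and no reported simulation covers the combination rule that will be run

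*Combined protocol and SAP*

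**What the plan says.** **Rule to be run.** Under Appendix 7, Section 2.2.1, posterior information on the BMS-986242 parameters "from the monotherapy Lead in will be used as marginal BMS-986242 prior for combination with nivolumab". Protocol Section 5.1.2.1 adds that "The initial dose level of BMS-986242 will be 12.5 mg administered orally daily" and, of the monotherapy and combination recommendations, that "The lower dose from these 2 recommendations will be considered". It also limits any increase to 100%, with about 4 participants first at each level and then increments of about 3.

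**Rule simulated.** Section 2.2.1 says that in the simulation the Table 1 prior "is used for illustration purposes because no real-time DLT data are available at this time". Section 3.1 says "The provisional dose levels for BMS-986242 monotherapy are 25 mg through 600 mg", with a fixed cohort size of 3. Its parameter list contains neither the lower-of-two rule nor the 100% cap.

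**Conclusions drawn.** Section 3.2.2 says that "the model performs well by correctly identifying the MTD ranging from 49% to 72% in the hypothetical scenarios investigated". Protocol Section 10.1.1 notes that the results are based on doses from 25 mg and that "an addition of 12.5 mg is expected to provide similar operating characteristics".

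**Interaction prior.** Appendix 7, Section 2.2.3 gives γ1 a gamma distribution with mean 1.1 and 97.5th percentile log(3). It describes that percentile as a 3-fold increase in DLT odds over independence at the starting dose, and puts 40% prior probability below 1.

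**The concern.** The MTD is a primary objective of Part 1, and Table 5 is the only operating-characteristics table for the combination model. If the table describes a rule that differs from the planned one in its prior, starting dose and possibly its selection step, its percentages cannot be taken as the planned rule's performance.

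The stated reason for leaving out lead-in data, that none exist yet, does not prevent simulating them. Table 4 already generates lead-in DLTs at true rates of 2% to 30%, and Appendix 7, Section 4 notes that "there could be 0, 1, 2, or 3 DLTs observed in the monotherapy lead-in period".

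The γ1 prior governs how far combination toxicity may exceed independence. If its stated properties conflict, a reader cannot tell which prior the in-house code uses and cannot reproduce Table 5 or later dose recommendations.

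**Working it through.** **1. The γ1 prior.** A gamma distribution has two parameters, so any two stated properties fix the third. Here log(3) = 1.0986.

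| Properties imposed | Solution | Implied third property | Stated |
|---|---|---|---|
| Mean 1.1; P(γ1<1) = 0.40 | shape 13.5 | 97.5th percentile 1.76 | 1.10 |
| P(γ1<1) = 0.40; 97.5th percentile log 3 | shape 541 | mean 1.01 | 1.1 |
| Mean 1.1; 97.5th percentile log 3 | shape 0.0054 | P(γ1<1) = 97% | 40% |
| Mean 1.1; 97.5th percentile 3 (if the log is a slip) | shape 2.12 | P(γ1<1) = 54% | 40% |

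The stated percentile lies just below the stated mean. No row meets all three properties.

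**2. The 3-fold description.** The Section 2.1 formula is p = 1 − exp(−[a^(1/γ1) + b^(1/γ1)]^γ1), with a = −log(1−p_A) and b = −log(1−p_B). Independence is γ1 = 1. Take p_A = 2% (Table 4 at 25 mg) and p_B = 3.7% (Table 3 at the reference dose: 1/(1+e^3.269)).

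- γ1 = 1: p = 5.63%, odds 0.0597.
- γ1 = log 3: p = 5.99%, odds 0.0637, a ratio of 1.07.

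With p_A of 1–2% (1% is assumed) and p_B of 3.7–10% (10% is the initial median in Section 2.2.2), the ratio is 1.03 to 1.07. A 3-fold ratio needs γ1 of about 2.6 to 2.9.

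**3. Table 5 from its own rows.** Selection of doses with true rates in the target interval:

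- Additive: 23.6 + 24.6 + 23.6 = 71.8%.
- 25% higher: 8.7 + 26.4 + 29.8 = 64.9%.
- 50% higher: 7.9 + 10.7 + 29.5 = 48.1%, reported as 49%.

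Selection of doses with true rates of at least 33%: 9.8%; 12.9 + 2.6 = 15.5%; 24.5 + 5.4 + 0.2 = 30.1%. The text does not report these totals.

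**4. What the lead-in data do (approximate).** The five-parameter model was rebuilt from Tables 1 and 3 with the Section 3.1 stopping rules, cohorts of 3, one-level steps and 4,000 trials per cell (Monte Carlo standard error up to 0.8 points). Lead-in DLTs were drawn at the Table 4 by-prior rates. Ranges cover three γ1 readings (rows 1, 2 and 4 above) and nivolumab at one or two times its reference dose. The 25 mg start is kept.

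| | Table 5 | Rebuilt, no lead-in | Rebuilt, lead-in carried in |
|---|---|---|---|
| Additive: in target | 71.8% | 72–74% | 79–89% |
| 25% higher: in target | 64.9% | 63–71% | 71–76% |
| 25% higher: true rate ≥33% | 15.5% | 12–16% | 13–23% |
| 50% higher: in target | 48.1% | 51–54% | 35–45% |
| 50% higher: true rate ≥33% | 30.1% | 29–33% | 38–55% |

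A separate rebuild under the first γ1 reading agrees in direction. Under 50% higher toxicity, above-target selection goes from 28.7% to 38.8%, of which 33.2 points are at 200 mg, where the true rate is 34%. Adding lower-of-two then moves results by about 1 point.

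**5. Adding the 12.5 mg level and a first cohort of 4.** Assumed 12.5 mg rates are 1% alone and 11%, about 13.5% and 16.5% in combination. Across the same settings (800 trials per cell, standard error up to about 1.8 points), the 50% higher scenario gives 45–59% in target and 32–49% above it. Above-target selection is about 1–2% under additive toxicity and 8–15% in the 25% higher scenario. In the 50% higher scenario the assumed 16.5% makes 12.5 mg a fourth on-target dose, which helps the in-target figure.

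**The case against.** The strongest reply is that the plan is open about most of this. Section 2.2.1 calls the simulated prior illustrative, Section 10.1.1 says the results start from 25 mg, and the Section 3.2.2 conclusion is confined to the scenarios investigated. Figures 1 and 2 show the model after both lead-in and combination data, and Figure 3 covers escalation scenarios. The model only recommends; the final dose choice uses all available data. All of that stands. But Figures 1–3 are worked examples from 25 mg, not operating characteristics, and disclosing that a different rule was simulated does not supply results for the planned one.

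The lower-of-two rule and the cap are only absent from a list; the code is not shown, so one cannot say they were not applied. Table 5's participant counts (3.6 at 25 mg, 3.2 at 50 mg, against 3.1 and 0.2 in Table 4) suggest that levels were not skipped, so the cap may have been in force.

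The γ1 defect is also mainly one of specification under the listed rule. In the separate rebuild, the first two readings in the table give 52.5% and 51.6% in target in the 50% higher scenario.

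A reader might infer that the planned rule performs worse than Table 5 or is unsafe. The documents do not support that. Carrying in lead-in data improves target selection in two of the three scenarios, and the adverse shift is mostly at a dose one point over the 33% boundary. It is smaller with the 12.5 mg start and a first cohort of 4.

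**Conclusion.** Two points hold on the documents alone. First, the γ1 prior as described does not exist, and its 3-fold gloss does not follow from the stated percentile. Second, no reported simulation of the planned combination rule supports either the Section 3.2.2 conclusion or the expectation about 12.5 mg in Section 10.1.1. The lower limit of the reported range should be 48%, a small correction. The 30.1% above-target selection in the same row deserves stating beside it.

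The direction of the lead-in effect is consistent across reconstructions: better under additive toxicity, and more above-target selection under 50% higher toxicity with the 25 mg start kept. Its size rests on the assumed γ1 reading, nivolumab scaling, 12.5 mg rates and stopping details that the plan leaves open. It should not be quoted as the error in Table 5. The 12.5 mg expectation is unsupported by a reported run, not shown to be wrong. This should be fixed; it is a gap in the stated evidence, not a finding against the rule.

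**What to change.** 1. State one coherent γ1 prior by shape and rate, confirm which one the code uses, and correct the 3-fold description.
2. Change 49% to 48% in Section 3.2.2, and label Table 5 as run without lead-in data and from 25 mg.
3. Re-run lead-in and combination jointly as planned: 12.5 mg level, lead-in DLTs generated and carried in, lower-of-two rule, 100% cap, first cohort of about 4 and then about 3. Report selection in and above the target interval, the proportion with no MTD, and participants treated at true rates of at least 33%.
4. Restate or qualify the conclusions in Section 3.2.2 and Section 10.1.1 from those results.

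The cost is computing time and a text amendment to Appendix 7 and Section 10.1.1. The escalation rule itself does not change. Some restated figures may be less favourable than those now printed.
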